28 days after injection; SAEs, MAAEs, AEs leading to withdrawal, pregnancies, and AESI will be assessed throughout the study. All participants will be tested for the presence of SARS-CoV-2 antibodies at baseline and at Day 29 (primary immunogenicity endpoint). Participants in Part J will also be tested for the presence of SARS-CoV-2 antibodies at Day 15 (primary immunogenicity endpoint). Additional blood draws will be collected on Day 91 (Parts A.2, F, G, H, and J only), Day 181, and Day 366 (Parts A.1, B, C, D, F, and G only). In addition, active surveillance for intercurrent or breakthrough SARS-CoV-2 infection will occur throughout the study and reported as AEs (confirmed symptomatic infections will be reported as MAAEs if not SAEs). Participants with signs and symptoms meeting the CDC case definition for COVID-19 (21 Feb 2021 or most recent [<https://www.cdc.gov/coronavirus/2019-ncov/symptoms-testing/symptoms.html>]) will be asked to contact the site and undergo prompt assessment which will include RT-PCR testing (of a respiratory sample) to assess symptomatic COVID-19. Participants with any clinical or radiographic evidence of pneumonia will also undergo RT-PCR testing. Suspected COVID-19 cases will also be tested using a multiplex assay to assess for non-SARS-CoV-2 causes of upper or lower respiratory tract infection. Participants will have blood samples collected at scheduled study site visits during the study for immunogenicity assessments or other medical concerns according to the investigator's judgment.

Participants may experience AEs, to include symptoms of COVID-19, that necessitate an unscheduled visit. There may also be situations in which the investigator asks a participant to report for an unscheduled visit following the report of an AE. Additional examinations may be conducted at these visits as necessary to ensure the safety and well-being of participants during the study. Electronic case report forms should be completed for each unscheduled visit. In addition, participants may have blood samples collected at unscheduled visits for acute respiratory symptoms.

Peripheral blood mononuclear cells (PBMCs) may be collected for a subset of participants at selected sites at baseline (Day 1) and at Days 15, 29, and 91 to characterize the T-cell and B-cell responses against SARS-CoV-2 and variants.

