2. OBJECTIVES AND ENDPOINTS

This study consists of 9 parts: A (1, 2), B, C D, E, F, G, H, and J. The objectives and endpoints in each part are described in the tables below, Part E objectives and endpoints are described in a site-specific protocol amendment and are not covered in this global protocol amendment. The objectives and endpoints for Parts A (1, 2), B, C, and D are described below in [Table 1](#), [Table 2](#), [Table 3](#), [Table 4](#), and [Table 5](#), respectively, the objectives and endpoints for Part F (Cohorts 1 and 2) are described in [Table 6](#) and [Table 7](#), the objectives and endpoints for Part G are described in [Table 8](#), the objectives and endpoints for Part H are described in [Table 9](#), and the objectives and endpoints for Part J are described in [Table 10](#).

Table 1: Part A.1 – 50 µg mRNA-1273.211 and 100 µg mRNA-1273.211

Objectives	Endpoints
Primary	

 To evaluate the safety and reactogenicity of mRNA-1273.211 	
 Solicited local and systemic reactogenicity ARs during a 7-day follow-up period after vaccination Unsolicited AEs during the 28-day follow-up period after vaccination SAEs, MAAEs, AEs leading to withdrawal and AESI from Day 1 to EoS
Exploratory	

 To evaluate the immunogenicity of mRNA-1273.211 at selected timepoints post boost To assess for symptomatic and asymptomatic SARS-CoV-2 infection 	
 Immune response of mRNA-1273.211 against ancestral SARS-CoV-2 and SARS-CoV-2 variants including B.1.351 at selected timepoints post boost by GMT, GMFR and SRR Laboratory-confirmed symptomatic or asymptomatic SARS-CoV-2 infection will be defined in participants: 
 Primary case definition per the mRNA-1273-P301 (COVE) study Secondary case definition based on the CDC criteria: the presence of one of the CDC-listed symptoms (CDC 2022) and a positive RT-PCR test on a respiratory sample Asymptomatic SARS-CoV-2 infection is defined as a positive RT-PCR test on a respiratory sample in the absence of symptoms or a positive serologic test for anti-nucleocapsid antibody after a negative test at time of enrollment

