Cases are defined as participants meeting clinical criteria based both on symptoms for COVID-19 and on RT-PCR detection of SARS-CoV-2 from samples collected within 72 hours of the study participant reporting symptoms meeting the definition of COVID-19. Participants who are hospitalized for COVID-19 without the opportunity for a clinic visit will also be considered cases, assuming that the symptomatology criteria for COVID-19 are met and a respiratory sample is positive for SARS-CoV-2 by PCR at a Clinical Laboratory Improvement Amendments (CLIA)-certified or CLIA-certified waiver laboratory. Investigators are encouraged to try to obtain a respiratory sample during the course of hospitalization for submission to the study central laboratory, if feasible.

Symptomatic COVID-19 is defined by the presence of one of the CDC-listed symptoms ([CDC 2020](#)) and a positive RT-PCR test on a respiratory sample. Asymptomatic SARS-CoV-2 infection is defined as a positive RT-PCR test on a respiratory sample in the absence of symptoms or a positive serologic test for antinucleocapsid antibody after a negative test result at the time of enrollment, with the serologic assay detecting previously resolved SARS-CoV-2 infections that may have occurred between visits, and the RT-PCR to detect active viral infection at the time of a visit. If participants are confirmed to have SARS-CoV-2 infection and are symptomatic or asymptomatic, the investigator will notify the participants' primary care physicians of the diagnosis and the local public health authorities as required per local regulations.

If the participant had known exposure to COVID-19 (eg, exposure to someone with a confirmed case of COVID-19), it will be captured in the COVID-19 exposure form, and the participant will continue to follow all remaining study assessments as scheduled. Likewise, participants with a confirmed case of COVID-19 will continue to follow all remaining study assessments as scheduled.

Any confirmed symptomatic COVID-19 infection occurring in participants will be captured as an MAAE along with relevant concomitant medications and details about severity, seriousness, and outcome.

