7.4.4. Medically Attended Adverse Events

An MAAE is an AE that leads to an unscheduled visit to an HCP. This would include visits to a study site for unscheduled assessments (eg, abnormal laboratory follow-up, COVID-19 [[Section 7.1.6](#)]) and visits to HCPs external to the study site (eg, urgent care, primary care physician). Investigators will review unsolicited AEs for the occurrence of any MAAEs. Unsolicited AEs will be captured on the AE page of the eCRF.

All confirmed COVID-19 cases will be recorded as MAAEs.

All suspected cases of anaphylaxis should be recorded as MAAEs and reported as an SAE, based on the criteria for a medically important event, unless the event meets other serious criteria. As an SAE, the event should be reported to the Sponsor or designee immediately and in all circumstances within 24 hours per [Section 7.4.11](#). The investigator will submit any updated anaphylaxis case data to the Sponsor within 24 hours of it being available. For reporting

purposes, a participant who displays signs or symptoms consistent with anaphylaxis (as follows) should be reported as a potential case of anaphylaxis. This is provided as general guidance for investigators and is based on the Brighton Collaboration case definition ([Rüggeberg et al 2007](#)).

Anaphylaxis is an acute hypersensitivity reaction with multi-organ system involvement that can present as, or rapidly progress to, a severe life-threatening reaction. It may occur following exposure to allergens from a variety of sources.

Anaphylaxis is a clinical syndrome characterized by the following:

- Sudden onset AND
- Rapid progression of signs and symptoms AND
- Involves 2 or more organ systems, as follows:
 - **Skin/mucosal:** urticaria (hives), generalized erythema, angioedema, generalized pruritus with skin rash, generalized prickle sensation, and red and itchy eyes.
 - **Cardiovascular:** measured hypotension, clinical diagnosis of uncompensated shock, loss of consciousness or decreased level of consciousness, and evidence of reduced peripheral circulation.
 - **Respiratory:** bilateral wheeze (bronchospasm), difficulty breathing, stridor, upper airway swelling (lip, tongue, throat, uvula, or larynx), respiratory distress, persistent dry cough, hoarse voice, sensation of throat closure, sneezing, and rhinorrhea.
 - **Gastrointestinal:** diarrhea, abdominal pain, nausea, and vomiting.

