6.3.1.1. Incidence of Adverse Events

An overall summary of unsolicited TEAEs including the number and percentage of subjects who experience the following will be presented:

- Any unsolicited TEAEs
- Any serious TEAEs
- Any fatal TEAEs
- Any unsolicited medically-attended TEAEs
- Any unsolicited TEAEs leading to discontinuation from participation in the study
- Any unsolicited severe TEAEs
- Any unsolicited AESIs
- Any unsolicited non-serious TEAEs
- Any unsolicited severe non-serious TEAEs

The table will also include number and percentage of subjects with unsolicited TEAEs that are treatment-related per PI's assessment in each of the above categories.

In addition, separate listings containing individual subject adverse event data for unsolicited AEs, unsolicited TEAEs leading to discontinuation from participation in the study, serious AEs and fatal unsolicited AEs will be provided separately.

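### The Synopsis and Section 3.1 make COVID-19 an MAAE only when it is not an SAE, while Sections 7.1.6 and 7.4.4 make every confirmed case an MAAE, so MAAE counts could depend on which section a site followed

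*Protocol*

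**What the plan says.** Two rules for COVID-19 stand in the current protocol.

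- **Synopsis (Overall Study Design) and Section 3.1.** In a bracket on surveillance for breakthrough infection, both say: "confirmed symptomatic infections will be reported as MAAEs if not SAEs".
- **Section 7.1.6.** "Any confirmed symptomatic COVID-19 infection occurring in participants will be captured as an MAAE along with relevant concomitant medications and details about severity, seriousness". Seriousness is thus a detail recorded about the MAAE.
- **Section 7.4.4.** "All confirmed COVID-19 cases will be recorded as MAAEs". This is slightly wider than 7.1.6, which speaks of symptomatic cases, and it has no exception for SAEs.

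The general definition in Section 7.4.4 is: "An MAAE is an AE that leads to an unscheduled visit to an HCP". The same section says of another event: "All suspected cases of anaphylaxis should be recorded as MAAEs and reported as an SAE".

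The objectives tables in Section 2 put both categories in one primary safety endpoint, for example "SAEs, MAAEs, AEs leading to withdrawal and AESI from Day 1 to EoS" for Part A.1. SAP Section 3.1 applies the same endpoint to all parts. In the overall summary of SAP Section 6.3.1.1, serious TEAEs have one row, and "Any unsolicited medically-attended TEAEs" is another.

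**The concern.** In plain wording, the bracket treats MAAE and SAE as alternatives. A site that follows it need not record a COVID-19 hospitalisation as an MAAE. A site that follows Section 7 must. MAAEs are a named component of the primary safety endpoint and have their own rows in Protocol Table 16 and in SAP Sections 6.3.1.1 and 6.3.1.2. Those rows could therefore rest on two reporting rules, one of which omits the serious COVID-19 cases.

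The classification matters more for COVID-19 than for most events. Unsolicited AEs in general are collected for only 28 days, and Appendix 4 says that COVID-19 itself is not an AESI. After Day 28 an infection enters the primary safety endpoint mainly as an MAAE or an SAE.

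**Working it through.** The plan states no figure on this point, so there is none to reproduce. The check sets the passages side by side and then bounds the effect.

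**1. How a serious, confirmed, symptomatic case is classified**

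| Source | MAAE? | SAE? |
|---|---|---|
| Synopsis and Section 3.1, read literally | No | Yes |
| Section 7.1.6 | Yes, with seriousness as a detail | Yes |
| Section 7.4.4, COVID-19 sentence | Yes | Yes |
| Section 7.4.4, general definition | Yes, if it led to unscheduled care | Yes |

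The bracket is the outlier. The anaphylaxis rule shows that one event may carry both labels. SAP Section 6.3.1 also treats medically attended status as something that can coexist with an AE's other attributes.

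**2. Whether the SAP settles it**

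SAP Section 1 says that the SAP prevails where its methods differ from the protocol's. However, SAP Section 6.3.1 leaves MAAE status to the investigator and has no rule specific to COVID-19. The investigator is the person holding both instructions.

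**3. What changes in the counts**

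For one arm, let S be the participants with any SAE, M the participants with any MAAE under the Section 7 rule, and D the participants whose only MAAE is a serious COVID-19 case. Under the literal bracket:

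- Participants with an MAAE = |M| − |D|.
- Participants with an SAE = |S|, unchanged.
- Participants with an SAE or an MAAE = |S ∪ M|, unchanged, because everyone in D is also in S.

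The loss in the participant-level MAAE row is therefore at most |D|, reached only if every site used the literal bracket. It cannot exceed the number with serious COVID-19. The number of MAAE events, which Table 16 also asks for, could be lower by the number of serious COVID-19 events.

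**4. Scale**

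Neither document gives a rate of serious COVID-19, so |D| cannot be computed. The weight of one affected participant follows from the planned arm sizes: 100/584 = 0.17, 100/500 = 0.20, 100/375 = 0.27 and 100/300 = 0.33 percentage points. In a Part J arm of about 50 it is 100/50 = 2.0 percentage points.

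**The case against.** The strongest reply is that the sections governing recording already give a clear rule. The Synopsis and Section 3.1 are overviews, and the words are a parenthesis. Sections 7.1.6 and 7.4.4 are the operative text, and a hospitalised case meets the MAAE definition in any event. The bracket can also be read as a minimum classification, meaning at least an MAAE and possibly an SAE, which would agree with Section 7. The SAP's allowance for coexisting MAAE status points the same way.

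Much of this stands. It makes a real undercount less likely, and it shows which way the text should be aligned. It does not remove the conflict. The minimum reading is possible but is not the plain one, the conditional appears in two places, and nothing says which section governs.

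Two stronger readings are tempting, and the documents support neither.

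- **A reader might infer that the most serious cases leave the primary safety endpoint.** They do not. A case is left out as an MAAE only because it is an SAE. SAEs sit in the same endpoint over the same period, with their own summary row, listing and tables by system organ class and preferred term.
- **A reader might infer that arms opened at different times were counted differently.** Enrolment was largely sequential, but both wordings apply to all parts in this protocol version. Nothing shows that practice changed by part or date.

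Nor do separate SAP rows make the categories exclusive. The serious, fatal, severe and medically attended rows plainly overlap.

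**Conclusion.** The inconsistency is real and should be corrected, as a minor point. Read literally, the Synopsis and Section 3.1 understate one named component of the primary safety endpoint relative to the protocol's own MAAE definition, and the count could vary with the section a site used. Variation between sites is possible but not shown.

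The size cannot be estimated from the documents. It is probably small, because only participants with serious COVID-19 and no other MAAE affect the participant-level row. SAE counts and the number of participants with either event are untouched. Protocol Section 8.5.4 makes all safety analyses descriptive, so no hypothesis test is affected. The conclusion assumes that at least some sites took the bracket literally. If none did, the tables are already right and the correction only removes the ambiguity.

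**What to change.** - **Protocol Synopsis and Section 3.1.** Reword the bracket so that confirmed symptomatic infections are reported as MAAEs, and also as SAEs if serious. This matches Sections 7.1.6 and 7.4.4.
- **SAP Section 6.3.1.** Add that every confirmed symptomatic COVID-19 AE, serious or not, is counted as medically attended in the MAAE tables. Use the symptomatic definition in Protocol Section 7.1.6 from Day 1. The efficacy counting rule in SAP Section 6.5.1.3 starts 14 days after injection and would miss early cases.

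The cost is one sentence in two places of the protocol and one programmed derivation. The derivation works on data already collected, so it makes the MAAE tables uniform whichever section a site followed. It should be in place before database lock, by which time Protocol Section 8 requires the SAP to be final. MAAE percentages may rise slightly; SAE tables do not change.
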